### **1.1.2 Atrial Fibrillation Classification**

Atrial Fibrillation is also known to be a progressive disease which can potentially be controlled with medication in its most benign state but can progress to be intractable. In an effort to bring uniformity to the various degrees that AF can present, the Heart Rhythm Society (HRS) 2017 AF expert consensus statementvii has recommended the following AF classification scheme based upon the patterns of duration and mode of termination:

Paroxysmal: Recurrent AF ( $\geq 2$  episodes) that terminates spontaneously within seven days. Episodes of AF of <48-hours duration that are terminated with electrical or pharmacologic cardioversion should also be classified as paroxysmal AF episodes.

Persistent: Continuous AF which is sustained beyond seven days.

Longstanding Persistent: Continuous AF of greater than 12-months' duration.

Permanent: Patients with AF in whom a decision has been made not to pursue restoration of sinus rhythm by any means.vii

This classification system has been recognized by FDA as part of their guidance documents regarding treatment of patients with AF.

### **1.1.3 Atrial Fibrillation Treatment**

AF is typically first treated with drug therapy, with an approximately equal split between rate and rhythm control drugs as first line of treatment. Recent large-scale studies have failed to show superiority of one treatment approach - rate or rhythm control - over another. Regardless of rate or rhythm control, continuous anticoagulation therapy is crucial in AF patients for stroke prevention. The AFFIRM study concluded that the benefit of restoring sinus rhythm in the rhythm control group was reversed by the toxicity of the antiarrhythmic drugs and hypothesized that if a treatment was available to restore sinus rhythm without the toxicity of antiarrhythmic drugs, survival may be improved.

Drug therapy failure may be due to either a lack of medication efficacy and/or a patient's inability to tolerate medications known to have serious and bothersome side effects, including those resulting from interactions with other drugs. According to its package insert, Cordarone® (amiodarone), the most widely prescribed anti-arrhythmic medication (not approved for the treatment of AF), is discontinued in 7-18% of patients due to intolerable side effects.

Surgical treatment of AF is usually considered when a patient is already scheduled for a concomitant cardiac procedure requiring access to the thoracic cavity. When performed concomitantly, the surgical treatment of AF is often performed using cardiopulmonary bypass on an open and arrested heart. The surgeon is unable to observe atrial function and cannot confirm treatment success intraoperatively because the atria must be beating in order to place a pacing electrode and confirm conduction block.

The Maze procedures (and its derivatives, Maze III, etc.), are considered the comparative standard for the effective treatment of AF. The Maze III procedure requires stopping the heart and then surgically cutting and re-sewing the atria to create a complex pattern of lesions throughout the atria that are intended to block macro-reentry circuits within the atria. In the intervening years, the Maze III procedure has been modified, but it remains the standard for treatment of atrial fibrillation. However, associated procedural mortality (2 to 10%) and morbidity including permanent pacemaker requirements (~15% of patients) have hindered the adoption of “cut and sew” procedure.

There have been many attempts to move away from the complexity and risk of the cut and sew Maze III procedure. Most of the effort has focused on procedures to isolate errant conduction signals that are suspected to originate from the pulmonary veins either by segmental ostial ablation or by the creation of a box lesion around the pulmonary veins. Electrically isolating the pulmonary veins may be effective for focal AF patients who have paroxysmal AF with no structural heart disease. However, more complex types of AF require a more comprehensive lesion pattern to block all reentrant circuits, and therefore sole isolation of the pulmonary veins is not an effective treatment.

To date, a percutaneous catheter-based or minimally invasive surgical procedure that can effectively and safely treat symptomatic longstanding persistent Atrial Fibrillation (AF) is unavailable.

The ideal treatment for AF would mitigate the detrimental sequelae of AF; that is, the procedure would restore normal sinus rhythm and cardiac hemodynamics, prevent continued remodeling and enlargement of the atria, and reduce the risk of thromboembolism. The ideal procedure would provide a means for assessing completeness of the lesion patterns. Continuous and complete lesions created throughout the atria and electrically silencing the posterior left atrium as well as isolating the pulmonary veins are most likely to prevent propagation of electrical signals capable of inducing and/or maintaining AF and prevent development of new reentrant circuits or atrial enlargement. The ideal procedure would also be performed utilizing minimally invasive, closed chest techniques.

#### **1.1.4 Cryoablation**

Cryosurgical ablation is defined as the use of a certain temperature below freezing to obtain a specific tissue response. The severity of the tissue response and destruction is directly related to the intensity of the freezing temperature. The mechanism of action of the use of freezing temperatures is that there is direct cell necrosis and vascular stasis which occurs only during the thawing period. The 4 stages areix

1. Acute intracellular freezing and cell necrosis.
2. Vascular stasis.
3. Dehydration in the thawing period via osmosis due to ion imbalance between intracellular and extracellular fluid.
4. Finally, latent apoptosis which takes several days longer and can last for days.

The major advantages of cryotherapy are: 1) visual confirmation of trans-murality by “ice ball” formation; 2) rapid creation of focal lesion; and 3) low risk of injury to adjacent tissues.x

### **1.1.5 Rationale for Conducting this Clinical Investigation**

This study is proposed herein is to gather clinical data on the safety and performance of the CRYOF device used in concomitant cardiac procedures.

Specifically, data from this study will be used for submission to regulatory authorities in Europe, China and other geographies as needed.

## **2 CLINICAL INVESTIGATION OVERVIEW**

### **2.1 Clinical Investigation Objective**

The primary objective of this study is to evaluate the safety and performance of the CRYOF device. The performance of the device will be demonstrated by establishing that the device effectively eliminates persistent and long-standing persistent atrial fibrillation in a clinically significant proportion of treated patients.

Treated subjects will be assessed for primary safety through 30-days post-procedure. Primary performance will be assessed at least through the 12-months post-procedure visit.

The minimum follow-up window will be at 12-months, with a maximum follow-up window at 24-months.

### **2.2 Investigational Device(s) To Be Used in the Clinical Investigation**

The subject device for this study will be the AtriCure cryoICE cryoablation system, which has been cleared under the 510 (k) process by the FDA and is approved in the UK and EU for commercial use. It is therefore not an investigational device.

The AtriCure cryoICE cryoablation system is comprised of:

- cryoICE® cryoFORM™ cryoablation probe, CRYOF
- AtriCure® Cryo Module (ACM1/ACM2)

#### **2.2.1 Name of the Device(s) Under Investigation**

Please refer to the IFU for additional information regarding the device used in this clinical investigation.

#### **2.2.2 Indication for Use**

The AtriCure cryoICE cryoFORM cryoablation probe is indicated for use in the cryosurgical treatment of cardiac arrhythmias by freezing target tissues, creating an inflammatory response (cryonecrosis) that blocks the electrical conduction pathway.

#### **2.2.3 Description of the Device(s) Under Investigation**

Please refer to the IFU for additional information regarding the device used in this clinical investigation.

#### **2.2.4 Device Handling**

Subjects enrolled in this study will already have been treated, therefore device accountability is not required.

### **3 CLINICAL INVESTIGATION DESIGN**

This is a retrospective-prospective, multi-center, non-randomized, unblinded, post-market study sponsored by AtriCure, Inc. This study will be conducted in the US, UK, and/or EU under a single protocol approved by an IRB/EC for each site prior to implementation at the study site. The Principal Investigators (PIs) bear the responsibilities described in the Protocol Signature Page.

The PIs at the sites are cardiac surgeons, qualified by education, experience, and training to assume responsibility for the conduct of this study. Up to 20 sites will participate in the study.

Up to 150 subjects will be enrolled as part of the study. Treated subjects will be assessed for primary safety through 30-days post-procedure. Primary performance will be assessed at at least 12-months post-procedure.

The minimum follow-up window will be at 12-months, with a maximum follow-up window at 24-months.

An independent Core Lab will be utilized for evaluation of the rhythm assessments. All assessments shall be performed in accordance with the core laboratory's recommended protocol which is provided to the sites in the Study Reference Manual.

An Electronic Data Capture (EDC) system will be utilized by study site personnel to transfer study data from source records (medical records and/or source document worksheets) onto common electronic case report forms (eCRFs). This system is a web-based, secure electronic software application, (Clindex®) developed and maintained by Fortress Medical Systems in a manner that is compliant with national and international GCP data protection/data privacy and electronic record/electronic signature (e.g., 21 CFR Part 11) regulatory requirements.

Adverse Events and medical device quality problems (for medical devices used during the procedure), including potential and actual device-related adverse events, certain malfunctions and user errors suspected to be associated with the use of a Food and Drug Administration (FDA) regulated drug, biologic, medical device or dietary supplement used during the course of this study will be reported by the PI to applicable authorities including the: 1) Sponsor (AtriCure); 2) IRB/EC; 3) respective manufacturer(s); and/or 4) FDA via MedWatch Online Voluntary Reporting Process or Medical Device Reporting as appropriate.

Critical decisions related to the design and execution of the study will be managed by a Study Oversight Committee.

The clinical investigation has been designed to involve as little pain, discomfort, fear, and any other foreseeable risk as possible for subjects. Refer to the Risks Analysis section of this protocol for details.

#### **3.1 Clinical Investigation Procedures and Follow-up Schedule**

Clinical investigation sites that have treated subjects with the CRYOF surgical ablation system will be approached to determine if they are resourced and willing to consent subjects treated within the past 24-months post procedure for rhythm assessment via 24-hr rhythm monitoring.

The goal of this study is to collect data for patients in which the CRYOF device was used to produce a set of lesions that are based upon the standard Cox-Maze III lesion set (hereinafter referred to as “the optimum lesion set”), consisting of the following lesions:

#### Right Atrial lesion set

Lesion	Endo/Epi	Device(s)	Minimum Duration
Atriotomy, extending from RA free wall near AV groove, to between SVC and IVC	Endo	NA	NA
Posterior RA, from midway between SVC-IVC up to the orifice of the SVC	Endo	CRYOF	2 min
Inferior lateral RA, from midway between SVC-IVC down to the orifice of the IVC	Endo	CRYOF	2 min
Extend T lesion down to posterior-lateral tricuspid annulus	Endo	CRYOF	2 min
Lesion from RAA to tricuspid valve annulus (10 o'clock)	Endo	CRYOF	2 min

#### Left Atrial lesion set

Lesion	Endo/Epi	Device(s)	Minimum Duration
Posterior inferior wall of the LA encircling left inferior pulmonary vein	Endo	CRYOF	2 min
Posterior superior wall of LA encircling left superior pulmonary vein	Endo	CRYOF	2 min
From the wall of LA to posterior mitral valve annulus	Endo	CRYOF	2 min
From LAA orifice to left pulmonary veins	Endo	CRYOF	2 min

#### Coronary Sinus lesion

Lesion	Endo/Epi	Device(s)	Minimum Duration
Epicardial lesion down to the level of mitral valve annulus with the inclusion of coronary sinus. **Ensure removal of retrograde cannula prior to lesion	Epi	CRYOF	2 min

If, for whatever reason, not all above mentioned lesions were performed, data will be collected on the actual lesions performed in order to allow subgroup analysis of patients that received the optimum lesion set, against patient that received a sub-optimum lesion set.

The LAA, however, should have been managed/excluded in all subjects ideally using the AtriCure AtriClip ACH1, ACH2, or FLEX V devices. Suture techniques are allowed as well.

The follow-up assessment data will be entered into the EDC developed for the study.

Documentation and reason for screen failure (i.e., inability to consent, refused consent, did not meet inclusion exclusion criteria, death or major morbidity (such as stroke) etc.) will be secured on a screening log within the EDC.

### **3.2 Measures Taken to Avoid and Minimize Bias**

This is a single-arm study. All enrolled subjects would have had a surgical ablation with the CRYOF device. Study data will be monitored against relevant source documents. An independent physician will adjudicate the SAEs reported in the study and rhythm assessments will also be adjudicated by a core lab. Furthermore, to mitigate temporal bias, enrollment in the trial will be based on random selection of treated subjects. The sequence with which treated subjects will be invited to participate in the trial will be randomly generated by the sponsor and provided to each site.

### **3.3 Suspension or Early Termination of the Clinical Investigation**

The Sponsor reserves the right to discontinue the clinical investigation at any stage or reduce the follow-up period with suitable written notice to the investigator. Possible reason(s) may include, but are not limited to:

- Unanticipated adverse device effect (e.g., UADE) occurs and it presents an unreasonable risk to the participating subjects
- A Study Oversight Committee (e.g., National PI(s) & AtriCure Medical Advisor) makes a recommendation to stop or terminate the clinical investigation.

Should the clinical investigation be discontinued by the Sponsor, subjects will be followed per routine hospital practice with device-related AEs reported to the Sponsor as per vigilance/commercial reporting requirements. All applicable clinical investigation documents shall be subject to the same retention policy as detailed in [Section 11.5] of the Protocol.

A Principal Investigator, IRB/EC or regulatory authority may suspend or prematurely terminate participation in the clinical investigation at the investigational site(s) for which they are responsible. The investigators will follow the requirements specified in the Clinical Trial Agreement.

If the Sponsor suspends or prematurely terminates the clinical investigation at an individual site in the interest of safety, the Sponsor will inform all other Principal Investigators.

If suspension or premature termination occurs, the Principal Investigator or authorized designee will promptly inform the enrolled subjects at his/her site, if appropriate, and return subjects to their standard medical treatment.

## **4 ENDPOINTS**

### **4.1 Primary Safety Endpoint**

This composite safety endpoint includes surgical ablation procedure related to death, stroke (regardless of level of disability), myocardial infarction, and major bleeding events within 30-days of the index ablation procedure. Deaths beyond 30-days and through last follow up that are attributed to surgical ablation procedure or CRYOF would be reported as Major Adverse Events (MAEs).

All MAEs will be adjudicated by an independent physician, thus maintaining the objectivity of the primary safety endpoint. A detailed definition of the MAEs is provided below:

- Excessive Bleeding: is defined as a major complication if it is subsequent to a device related or study procedure-related injury and is treated with transfusion or results in a 20% or greater fall in HCT. Transfusion for anemia or other pre-existing condition that cause a fall in HCT without acute bleeding will not be considered a Major Adverse Event. Documentation of the cause of the bleed, and transfusion, and/or 20% or greater drop in HCT.
- Myocardial infarction (MI): When low blood flow causes the heart to starve for oxygen. Heart muscle dies or becomes permanently damaged. Documentation of MI; the presence of any one of the following criteria: (1) detection of ECG changes indicative of new ischemia (new ST-T changes or new LBBB) which persist for more than 1 hr, (2) development of new pathological Q waves on an ECG, and (3) imaging evidence of new loss of viable myocardium or new regional wall motion abnormality.
- Stroke: A stroke is an interruption of the blood supply to any part of the brain. Rapid onset of a focal or global neurological deficit with at least one of the following: change in level of consciousness, hemiplegia, hemiparesis, numbness or sensory loss affecting one side of the body, dysphasia or aphasia, hemianopia, amaurosis fugax, or other neurological signs or symptoms consistent with stroke. Duration of a focal or global neurological deficit  $\geq 24$  h; OR  $<24$  h if therapeutic intervention(s) were performed (e.g., thrombolytic therapy or intracranial angioplasty); OR available neuroimaging documents a new hemorrhage or infarct; OR the neurological deficit results in death AND no other readily identifiable non-stroke cause for the clinical presentation (e.g., brain tumor, trauma, infection, hypoglycemia, peripheral lesion, pharmacological influences). Diagnosis should be confirmed by a neurology or neurosurgical specialist utilizing a neuroimaging procedure (MR or CT scan or cerebral angiography) or lumbar puncture (i.e., spinal fluid analysis diagnostic of intracranial hemorrhage). Documentation of a stroke or CVA consisting of acute loss of neurological function caused by an ischemic event with residual symptoms at least 24 hours after onset confirmed by CT or MRI scan or cerebral angiography of acute neurological event.
- Transient Ischemic attacks (TIA): A transient ischemic attack is a "mini-stroke" caused by temporary disturbance of blood supply to an area of the brain, which results in a sudden, brief decrease in brain function. Clinical symptoms similar to stroke but last for less than 24 hours. Documentation of TIA neuroimaging without tissue injury consistent with acute loss of neurological function caused by an ischemic event with resolution of symptoms within 24 hours after onset.
- Death: Document cause of death and include autopsy findings if autopsy performed.

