Subject Follow-up	
Treated subjects will be assessed for primary safety through 30-days post-procedure. Primary performance will be assessed at at least 12-months post-procedure.
 
The minimum follow-up window will be at 12-months, with a maximum follow-up window at 24-months.

Primary Endpoint(s)	
Primary Safety Endpoint:
 
The composite safety endpoint includes surgical ablation procedure related to death, stroke (regardless of level of disability), myocardial infarction, and major bleeding events within 30-days of the index ablation procedure. Deaths beyond 30-days and through last follow up that are attributed to surgical ablation procedure or CRYOF will also be reported as MAEs.
 
The reported events will be adjudicated by an independent physician for severity and relatedness to device and/or procedure.
 
Primary Performance Endpoint:
 
The primary performance endpoint is freedom from any documented atrial fibrillation (AF), atrial flutter (AFL), or atrial tachycardia (AT) lasting >30 seconds in duration at the last follow-up visit in the absence of Class I or III AADs (with the exception of AADs at doses not exceeding those previously failed). The rhythm status used for evaluation of this endpoint will be derived from a 24-hours electrocardiographic rhythm monitoring. The minimum follow-up window is 12 months and maximum at 24 months.
 
Any of the following scenarios will be captured and reported as failure of this effectiveness endpoint:
 
 
• Any electrocardiographically documented AF, AFL or AT recurrences lasting >30 seconds in duration at the last follow-up visit (by 30 second 12-lead ECG or 24-hours continuous ECG monitoring);
 

	
 
• The use of either new Class I or III antiarrhythmic drugs or doses exceeding previously failed (i.e. prior to ablation) at the last follow-up visit;
 
• Any subsequent catheter ablation or surgical ablation treatment for AF, AFL or AT following the index surgical AF ablation procedure (except for treatment of right typical atrial flutter).
 

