#### **4.3 Secondary Safety Endpoint**

Key Secondary Safety Endpoints include:

- Implantation of a permanent pacemaker post-procedure through the last follow-up period.
- Overall device or surgical ablation procedure related SAEs through last follow up.

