### 7.4 Device Relationship

Determination of whether there is a reasonable possibility that an investigational product or device under investigation caused or contributed to an AE is to be determined by the Investigator and recorded on the appropriate CRF form. Determination should be based on assessment of temporal relationships, evidence of alternative etiology, medical/biologic plausibility, and subject condition (pre-existing condition).

It is the Investigator's responsibility to assess the relationship of an AE to the study procedure and/or device.

Adverse events will be assigned an attribution according to the Investigator's believed primary cause. Events will be categorized by relationship to the investigational device(s) listed in this protocol or ancillary device, surgical ablation procedure, general cardiac surgical procedure or subsequent intervention, concomitant medications, pre-existing condition, intercurrent condition, intercurrent intervention, or unknown.

The following guidelines should be used in determining the relationship of an adverse event to the study device or procedure:

- **Unknown:** A clinical event (including abnormal laboratory result) that cannot be determined to be related or unrelated to device/procedure/drug given information provided.
- **Device Related Adverse Event:** An adverse event, that in the judgment of the Investigator, resulted from use of the cryoICE® cryoablation system may have caused or contributed to the AE.
- **Procedure Related Adverse Event:** An adverse event which, in the judgment of the Investigator, results as a consequence of the investigational procedure and is not specifically related to the use of the cryoICE® cryoablation system.
- **General Surgery Related Adverse Event:** An adverse event which, in the judgement of the Investigator, results as a consequence of general cardiac surgical procedural complications and/or subsequent interventions.
- **Concomitant Medication-Related Adverse Event:** An adverse event is considered to be concomitant medication related when, in the judgment of the Investigator, it is reasonable to believe that the event is associated with concomitant medications used in conjunction with the investigational device and is not otherwise specific to the investigational device (e.g. bleeding associated with anticoagulation medication).

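### The attribution scope of the 30-day primary safety composite is contradictory, and on the literal reading a stroke or MI attributed to the device is not counted

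*Combined protocol and SAP*

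**What the plan says.** The protocol describes which 30-day events count in several ways.

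- **Section 4.1, opening sentence:** "This composite safety endpoint includes surgical ablation procedure related to death, stroke (regardless of level of disability), myocardial infarction, and major bleeding events within 30-days". The synopsis agrees: "The composite safety endpoint includes surgical ablation procedure related to death, stroke (regardless of level of disability), myocardial infarction, and major bleeding events". The grammar is broken, but the only attribution named is the surgical ablation procedure.
- **Section 4.1, late deaths:** "Deaths beyond 30-days and through last follow up that are attributed to surgical ablation procedure or CRYOF would be reported as Major Adverse Events". Here the device is named.
- **Section 4.1, bleeding definition:** the bleed must be "subsequent to a device related or study procedure-related injury". The device is named again. The definitions of MI, stroke, TIA and death in the same section carry no relatedness condition.
- **Section 4.3, secondary safety endpoint:** "Overall device or surgical ablation procedure related SAEs through last follow up".
- **Section 7.4:** "Events will be categorized by relationship to the investigational device(s) listed in this protocol or ancillary device, surgical ablation procedure, general cardiac surgical procedure", with attribution by primary cause. A procedure-related event is one that "results as a consequence of the investigational procedure and is not specifically related to the use of the cryoICE® cryoablation system".
- **Sections 7, 7.1.1 and 8.2.2:** all use the MAE list of section 4.1 and add no attribution limit of their own.
- **Synopsis, adjudication:** an independent physician judges relatedness to the device, the procedure or both.

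**The concern.** The primary objective is the safety of CRYOF, and the results are intended for regulatory submission. Section 7.4 treats device and procedure as separate attributions. If the opening sentence of 4.1 is applied with that definition, a stroke or MI that the adjudicator assigns to the device does not qualify as procedure-related and leaves the numerator tested against 15%. The events most directly informative about the device would then be the ones missing from its primary safety test.

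The direction is fixed: leaving events out can only lower the observed MAE rate, so any error favours success. Because success of the study requires the safety test to be met, the rule for what counts in q needs to be unambiguous before the data are seen.

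**Working it through.** **1. What each part of the protocol implies for a 30-day event coded to the device**

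| Source | Attribution wording | Device-coded stroke or MI |
|---|---|---|
| Synopsis and 4.1, opening sentence, with 7.4 | procedure only | not counted |
| 4.1, definitions of stroke and MI | none | counted |
| 7 and 7.1.1 | none of their own; refer to 4.1 | counted, unless the opening sentence of 4.1 is inherited |
| 8.2.2 | none of its own; refers to 4.1 | same |

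The late-death sentence and 4.3 do not govern these events. They do show that the authors named the device in places where they meant to include it.

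**2. Which components are affected**

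- *Bleeding:* retained, because its own definition covers device-related injury.
- *Death within 30 days:* largely moot. Section 6.2.1 has subjects consented 12 to 24 months after the procedure, and section 5.3.2 requires their own consent and ability to return. A subject who died within 30 days could not be enrolled on that schedule.
- *Stroke and MI:* affected. Some stroke patients may also be lost earlier, since sections 3.1 and 5.2.1 list major morbidity such as stroke among the reasons for screen failure.
- *TIA:* defined in 4.1 and listed in 7.1.1, but absent from the opening sentence, so its status is open on a second ground.

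**3. Reproducing the plan's safety design**

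Inputs from sections 8.2.2 and 8.3: n = 150, goal 15%, one-sided α = 0.05, exact binomial test, expected rate 8.5%, stated limit 15/150, stated power 80%.

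- P(X ≤ 15 | 150, 0.15) = 0.0493, so 15 passes.
- P(X ≤ 16 | 150, 0.15) = 0.0807, so 16 fails.
- P(X ≤ 15 | 150, 0.085) = 0.794, in line with the stated 80%.

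The limit and the power are confirmed. The point concerns what is counted, not this calculation.

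**4. When the two rules give different verdicts**

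Let X be the number of subjects with an MAE under the procedure-only rule. Let D be the number whose only 30-day MAE is a device-coded non-bleeding event. The verdicts differ exactly when X ≤ 15 and X + D ≥ 16. With X = 15, D = 1 is enough.

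**5. Illustration of the effect on the false-pass probability**

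Assume a true rate of 15% over device- and procedure-related MAEs together, and one event type per subject. Let b be the share that is bleeding and d the device-coded share of the rest. Both are assumptions; the documents give neither.

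Counted rate = 0.15 × [b + (1 − b)(1 − d)], and P(pass) = P(X ≤ 15 | 150, counted rate).

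| b | d | Counted rate | P(pass) |
|---|---|---|---|
| any | 0 | 0.15 | 4.9% |
| 0.8 | 0.2 | 0.15 × 0.96 = 0.1440 | 7.3% |
| 0.7 | 0.3 | 0.15 × 0.91 = 0.1365 | 11.6% |
| 0.5 | 0.3 | 0.15 × 0.85 = 0.1275 | 18.9% |

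**The case against.** The best case on the other side is that the exclusion is an inference, not a stated rule. The opening sentence of 4.1 is garbled and does not cite 7.4. Section 7.4 speaks of the investigational procedure and governs the investigator's coding on the case report form, whereas endpoint events go to an independent adjudicator who considers the device as well as the procedure. The stroke and MI definitions have no relatedness condition, and sections 7, 7.1.1 and 8.2.2 add none. On that reading device-attributed events count.

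Much of this stands. A reader might infer that the plan definitely removes device-attributed events from the composite, and the documents do not support that. They support two readings.

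It does not remove the problem. Sections 7, 7.1.1 and 8.2.2 all send the reader back to 4.1, so they can be taken to inherit its opening sentence. Adjudicating both kinds of relatedness does not say which kind enters q. Section 7.4 is also the only place where procedure-relatedness is defined, so an adjudicator would naturally turn to it.

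Two further inferences should be resisted. One is that early device-caused deaths would be lost through this wording; the consent schedule means they can hardly enter the data at all. The other is a very large effect. Dropping 20% or 30% of all MAEs would raise the pass probability at a true 15% rate to about 27% or 49%. That would also remove device-related bleeding, which the protocol keeps, unless bleeding made up almost none of the events.

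**Conclusion.** The point holds as an unresolved contradiction in the definition of the primary safety endpoint. On the literal reading of 4.1 with 7.4, a 30-day stroke or MI attributed to the device is not counted in q; on other readings it is. Any omission favours a pass.

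The size cannot be established from the documents. A single subject reverses the result only if the narrower count is exactly 15, which is true of any exact-test boundary. The illustrative rise from 4.9% to 11.6%, and the range of 7.3% to 18.9% across the combinations shown, rest entirely on the assumed bleeding and device-coded shares and on a true rate equal to the 15% goal. The literature behind that goal is not described in enough detail to show which scope it reflects, so the documents do not settle whether the intended scope is any-cause or related events.

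**What to change.** Reconcile the synopsis and sections 4.1, 7, 7.1.1, 7.4 and 8.2.2 before database lock, so that device-attributed events count in q under whichever scope is chosen.

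- *If a relatedness limit is intended:* have 4.1 and the synopsis say that the events are related to the CRYOF device and/or the surgical ablation procedure. Carry the same limit into 7 and 7.1.1, and state in 8.2.2 that an event adjudicated to either category counts.
- *If any-cause events are intended:* delete the relatedness phrase from 4.1 and the synopsis, and align the bleeding definition with that choice.
- *In either case:* state whether TIA is a component, and confirm that the chosen scope matches the basis of the 15% goal and the 8.5% assumption.

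The sponsor should choose between these two. The first must not be adopted by default, because it would narrow the unrestricted wording of 7 and 7.1.1.

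The cost is a few lines of text. No new data are needed to count both attributions, since 7.4 already records them. The observed MAE rate may be slightly higher. If the 8.5% was set without device-attributed events, power would fall from 0.794 to 0.725 with an added 0.5 percentage points, or to 0.648 with an added 1 point; both additions are assumptions.
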